IVC filter	ACCP 2012	
 IVC filter should not be used for primary VTE prevention for all risk groups
	ASCO 2015	
 Not specified in primary prophylaxis setting
	ESMO 2011	
 Not specified in primary prophylaxis setting
Duration of thromboprophylaxis	ACCP 2012	
 Not specified
	ASCO 2015	
 7–10 d
	ESMO 2011	
 At least 10 d
Extended thromboprophylaxis	ACCP 2011	
 For high-risk patients undergoing abdominal or pelvic surgery for cancer who are not otherwise at high risk for major bleeding complications, extended duration pharmacologic prophylaxis (4 wk) with LMWH is recommended over limited-duration prophylaxis
	ASCO 2015	
 Extended prophylaxis with LMWH for up to 4 wk postoperatively should be considered for patients undergoing major abdominal or pelvic surgery for cancer who have high-risk features such as restricted mobility, obesity, history of VTE, or with additional risk factors
	ESMO 2011	
 Cancer patients undergoing elective major abdominal or pelvic surgery should receive in-hospital and postdischarge prophylaxis with LMWH for up to 1 mo after surgery

Abbreviations: IVC filter, inferior vena cava filter; LDUH, low-dose unfractionated heparin; LMWH, low-molecular-weight heparin; UFH, unfractionated heparin; VTE, venous thromboembolism.

Introduction for cancer patients undergoing chemotherapy

Venous Thromboembolism (VTE) is a frequent malignancy complication which often results in serious health deterioration and death. The risk of deep vein thrombosis (DVT) and pulmonary embolism (PE) is considerably higher in cancer patients, compared to general population four to seven times [23, 24]. Venous thromboembolism is the second leading cause of death in patients with cancer and overall mortality is increased among patients who have both conditions. [25, 26, 27]

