Moreover, chemotherapy and thrombosis for over three decades, it remains an underappreciated risk that has not been routinely incorporated into thrombosis risk assessment models.[42] Cytotoxic chemotherapy has a multifactorial contribution to the risk of thrombosis. It induces vascular injury through apoptosis. In the case of cisplatin, this leads to release of prothrombotic particles that trigger thrombin generation via tissue factor independent mechanisms along with drastically increased vWF activity. Other agents, like 5-FU, also drive thrombin formation in combination with depleted protein C activity. L-asparaginase administration is tied to drastically decreased protein C, protein S, and antithrombin levels, creating a prothrombotic milieu through loss of anticoagulant factors. VEGF inhibition does not directly lead to thrombosis, but instead 'primes' the endothelium through a VEGF starved state to be more susceptible to injury. Additionally, platelet activation through PAR-1 and increased Gp IIb/IIIa activity in the case of immunomodulatory agents or increased vWF among others in the case of small molecule inhibitors contributes to this 'primed' state.[43-81]

Cancer patients undergoing systemic treatment for their malignancy are among the highest risk populations for thromboembolic complications; often, the treatment itself contributes to this risk. Recognition of the antineoplastic agents most likely to cause thrombosis can help raise provider awareness and lead to earlier diagnosis and treatment.

In our approach, we will protect our patient taking under consideration their treatment (surgery either chemotherapy)

Study Objective

In this study we will collect Real World Data of our clinical practice regarding Thromboprophylaxis in high thrombotic risk solid tumors patients undergoing surgical and /or chemotherapeutical treatment, for one year following the protocol initiation date.

- **Specifically we will focus on the following :**
 - Number of thrombotic events
 - Anti-thrombotic management dosage & duration
 - Any bleedings related to anticoagulation
 - Patients' adherence and compliance

Study Design

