This is a prospective, phase IV, observational, non-interventional cohort study that aims to record the daily clinical practice regarding thromboprophylaxis in high thrombotic risk cancer patients (under surgery or chemotherapy) initiated December 2018 for a year time. Patients demographic data, cancer type and stage, anticoagulant treatment dose & duration, efficacy (VTE events), safety (bleedings) and information about adherence will be collected; more than one outcomes could be recorded.

Subject Completion/Withdrawal

Subjects may withdraw from the study at any time without prejudice to their care. They may also be discontinued from the study at the discretion of the Investigator for lack of adherence to study treatment or visit schedules, AEs, or due to termination of study observation period. The Investigator may also withdraw subjects who violate the study plan, or to protect the subject for reasons of safety or for administrative reasons. It will be documented whether or not each subject completes the clinical study. If the Investigator becomes aware of any serious, related adverse events after the subject completes or withdraws from the study, they will be recorded in the source documents and on the CRF.

Clinical Adverse Events

Clinical adverse events (AEs) will be monitored throughout the study.

Adverse Event Reporting

Since the study procedures are not greater than minimal risk, SAEs are not expected. If any unanticipated problems related to the research involving risks to subjects or others happen during the course of this study (including SAEs) these will be reported in accordance with current regulations. AEs that are not serious but that are notable and could involve risks to subjects will be summarized in narrative format.

Authorized staff will perform periodic site visits to review CRFs for completeness, but will have no direct access to patient records; although they could request further information from the hospital staff. The anonymized data will be collated centrally and entered into an electronic database using double data entry where appropriate. Any discrepancies identified by electronic logic checks and will be resolved using data clarification forms sent to sites.

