Ethics committee approval will be obtained where approval of a prospective non-interventional study is required. This study will be conducted in full accordance all applicable Research Policies and Procedures and all applicable laws and regulations. The investigators will perform the study in accordance with this protocol, will obtain consent, and will report unanticipated problems involving risks to subjects or others in accordance with Policies and Procedures and all regulatory

requirements. Collection, recording, and reporting of data will be accurate and will ensure the privacy, health, and welfare of research subjects during and after the study.

Subject Population **Inclusion Criteria**

key criteria for Inclusion and Exclusion:

1. Patients who were diagnosed with histological confirmed high thrombotic risk cancers (GI, thoracic, gynecologic and genitourinary) undergoing surgery
2. Age \geq 18 years

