3. ECOG 0-2
4. Life expectancy >6 months
5. Signed informed consent

Exclusion Criteria

1. Patients who were not diagnosed with histological confirmed high thrombotic risk cancers (GI, thoracic, gynecologic and genitourinary) undergoing surgery
2. Age $<$ 18 years

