3. ECOG >2
4. Life expectancy <6 months
5. Not signed informed consent

Study Duration	Each subject's participation will last from inclusion (enrolment visit) to follow up visit (if applicable; four weeks post hospital discharge) The entire study is expected to last by the end of 2019
Study Phases	(1) Screening : screening for eligibility, obtaining consent and administer thromboprophylaxis
Screening	
Study Treatment	(2) Observation Period : monitoring subjects over treatment time
Treatment	(3) Follow-up Phase (only if applicable e.g. by the end of treatment period)
Follow-Up	
Efficacy Evaluations	
 • Symptomatic/Suspected vein thromboembolism, including pulmonary embolism and deep vein thrombosis 
Confirmation of symptomatic PE requires symptoms of PE and one of the following findings
 
 1. A (new) intraluminal filling defect in (sub) segmental or more proximal branches on spiral CT scan; 2. A (new) intraluminal filling defect or an extension of an existing defect or a new sudden cut-off of vessels on the pulmonary angiogram;

3. A (new) considerable perfusion defect (~ 75% of a segment) with a local normal ventilation result (high-probability) on ventilation/perfusion lung scintigraphy (V/Q scan);
4. An inconclusive lung scan accompanied by documentation of (new) DVT in the lower extremities e.g., by compression ultrasound or venography.
 - Confirmation of symptomatic DVT requires symptoms of DVT and:
 - 1. A (new) noncompressible venous segment on ultrasonography
 - Incidental PE with one of the following:
 1. A (new) intra-luminal filling defect on CT scan, MRI scan, or pulmonary angiogram;
 - An inconclusive lung scan accompanied by documentation of (new) DVT in the lower extremities e.g., by compression ultrasound or venography.
 - Fatal PE is:
 1. PE based on objective diagnostic testing or autopsy or
 2. death not attributed to a documented cause and for which DVT/PE cannot be ruled out
 - Incidental DVT with the following finding:

Confirmation of recurrent incidental DVT requires inconclusive or no-symptoms of DVT and:

1. A (new) noncompressible venous segment on ultrasonography

Safety Evaluations Major, clinically relevant non-major bleeding, and minor bleeding

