Major bleeding will be defined as overt bleeding associated with: a fall in hemoglobin of 2 g/dL or more, or leading to a transfusion, or bleeding that occurs in a critical site or contributing to death.

- **Bleeding in a critical area or organ such as:**

Retroperitoneal

Intracranial

Intraocular

Intraspinal

Intra-articular

Pericardial

Intramuscular with compartment syndrome

- **A clinically overt bleeding event**
 - that is associated with a fall in hemoglobin of 2.0 g/dL (>1.24 mMol/L) or more, or
 - leading to a transfusion of ≥ 2 units of packed red blood cells or whole blood.
- **Bleeding contributing to death**

Other clinically relevant non-major bleeding will be defined as overt bleeding not meeting the criteria for major bleeding but associated with medical intervention, unscheduled contact (visit or telephone call) with a physician, (temporary) cessation of study treatment, or associated with discomfort for the patient such as pain, or impairment of activities of daily life. All other bleeding events will be classified as minor

Statistical And Analytic Plan	
Descriptional statistical analysis will be performed for all study data along with epidemiology methods. Continuing parameters will be presented with standards descriptional statistical measures (mean values, median values, percentages etc.) and the results will be presented accordingly into tables. For more complex correlations we will use, among other methods, chi-square tests, ANOVA and t-tests, in order to evaluate the relationships between different patient and disease characteristics, such as:
 
 • Number of patients enrolled • Tumor characteristics • Co-morbidities • Type of Surgical operation • Type of antineoplastic treatment • Type of thromboprophylaxis therapy • Therapy outcomes • Number of therapy disruptions for any reason • Complications (AE- SAE) 
and to present them, accordingly. Due to the fact that this is an observational study the results of all correlations will be carefully discussed and will be used only to assess hypotheses.

REFERENCES	References

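### Inclusion criterion 1 admits only surgical patients, although the objective and design also name patients treated with chemotherapy alone

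*Combined protocol and SAP*

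**What the plan says.** Three statements in the combined protocol and SAP set the population as surgery or chemotherapy:

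- The last sentence before the Study Objective: "we will protect our patient taking under consideration their treatment (surgery either chemotherapy".
- The Study Objective: "high thrombotic risk solid tumors patients undergoing surgical and /or chemotherapeutical treatment".
- The Study Design: "thromboprophylaxis in high thrombotic risk cancer patients (under surgery or chemotherapy".

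The background matches this. It has a separate part headed "Introduction for cancer patients undergoing chemotherapy", which covers ambulatory patients on chemotherapy and a risk score for them.

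Inclusion criterion 1, under Subject Population, is narrower: "Patients who were diagnosed with histological confirmed high thrombotic risk cancers (GI, thoracic, gynecologic and genitourinary) undergoing surgery". Exclusion criterion 1 is its negation: "Patients who were not diagnosed with histological confirmed high thrombotic risk cancers (GI, thoracic, gynecologic and genitourinary) undergoing surgery". The remaining criteria concern age, performance status, life expectancy and consent.

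**The concern.** The eligibility criteria are what a site applies when it decides whether to enrol a patient. If they are applied literally, no patient on chemotherapy without surgery enters the study, and part of the stated objective cannot be answered.

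If some sites follow the objective instead, they will enrol patients who fail criterion 1. The mix of settings in the cohort would then depend on how each site read the protocol. The Subject Completion/Withdrawal section lets the investigator withdraw subjects who violate the study plan, so the status of those patients would be unclear.

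In a descriptive cohort the eligible population is the denominator of every reported frequency. Here that denominator is defined in two incompatible ways.

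**Working it through.** No formula applies. The plan states no sample size, error rate, power or effect size, so there is no figure of its own to reproduce. The check sets the passages side by side.

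**Step 1: settings named.** The objective's and/or wording gives three settings. Reading the design's *or* inclusively, it covers the same three.

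| Setting | Objective | Design | Meets inclusion criterion 1 |
|---|---|---|---|
| Surgery only | yes | yes | yes |
| Surgery and chemotherapy | yes | yes | yes |
| Chemotherapy only | yes | yes | no |

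Settings named: 3. Settings admitted: 2. Settings shut out: 3 − 2 = 1.

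**Step 2: is there another route in?** Inclusion criteria 2 to 5 do not mention treatment and cannot substitute for criterion 1.

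**Step 3: does exclusion criterion 1 settle it?** It can be read in two ways. If the negation covers the whole phrase, a chemotherapy-only patient is excluded. If it covers only the cancer diagnosis, that patient is not excluded, but still fails inclusion criterion 1. Neither reading makes the patient eligible.

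**Step 4: does the analysis plan settle it?** The Statistical And Analytic Plan lists "Type of antineoplastic treatment" as a characteristic to analyse. Operated patients may also receive such treatment, so the variable is compatible with a purely surgical cohort and admits nobody new.

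**Step 5: what is lost.** The Study Objective lists four items: thrombotic events, dosage and duration of prophylaxis, bleeding, and adherence and compliance. With no eligible patients in the chemotherapy-only setting, 4 of 4 go undescribed there.

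**Step 6: follow-up.** The only timed visit, under Study Duration, is four weeks after hospital discharge, if applicable. The follow-up phase is also conditional: "only if applicable e.g. by the end of treatment period". This does not contradict criterion 1. It does leave the end of observation undefined for a patient who is never discharged, should such patients be admitted.

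**The case against.** The strongest reply is that three population statements and a whole background section point to chemotherapy patients being intended, so criterion 1 is probably a drafting omission that sites will read through. That may be so, but the surgical wording stands in both inclusion criterion 1 and exclusion criterion 1, so it cannot be assumed to be a single slip. Reading through it would also produce enrolments that depart from the written criteria. What stands is that the harm may run either way: a lost population, or a cohort whose composition varies by site.

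A second reply is that the list is headed as key criteria and may be incomplete. Unlisted criteria could add restrictions, but they would not waive a listed one.

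Third, the study is non-interventional and descriptive, and no powered test is undermined. That is true, and surgical patients, with or without chemotherapy, can still be described. It does not help the setting that cannot be enrolled.

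Fourth, the counts of settings and items only restate the text as fractions. This is fair: they mark the extent of the conflict and are not an effect size.

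Finally, reporting by setting and clarifying follow-up go beyond reconciling the words. They do, but both are modest. The follow-up wording already leaves some room for patients without a discharge, and the reporting relies largely on variables already planned. One caution stands: antineoplastic treatment is broader than chemotherapy, and the plan does not fix its timing relative to enrolment, so that variable alone may not classify every patient.

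**Conclusion.** The concern holds and must be fixed. The objective and design define one population and the eligibility criteria another. Under the criteria as written, one of the three named settings cannot be enrolled, and all four objective items go unanswered for it. These are counts of settings and items, not of patients. The number or share of patients affected cannot be derived from the document.

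The conclusion rests on the text available. The case report form is listed in the Appendix but was not available for review. It also assumes that sites apply the listed criteria literally. The document does not show which population the sponsor intends, so the choice is the sponsor's.

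**What to change.** Choose one of two routes.

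1. **Keep chemotherapy-only patients.** Reword inclusion criterion 1 to cover surgery and/or chemotherapy, and rewrite exclusion criterion 1 to match without its present ambiguity. Classify each patient as surgery only, chemotherapy only or both, using the planned data on type of operation and antineoplastic treatment, and define what counts as chemotherapy and over what period. Report thrombotic and bleeding events by setting. State how the existing observation and follow-up wording applies to patients with no hospital discharge. Cost: an amendment to two criteria, a clarification of the follow-up text, and a setting field on the case report form only if it does not already capture this.

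2. **Study surgical patients only.** Restrict the Study Objective, the Study Design and the closing sentence of the introduction to them. The chemotherapy background can remain as context if it is labelled so. Cost: wording only.

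Neither route changes any treatment given to patients.

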3. ECOG 0-2
4. Life expectancy >6 months
5. Signed informed consent

Exclusion Criteria

1. Patients who were not diagnosed with histological confirmed high thrombotic risk cancers (GI, thoracic, gynecologic and genitourinary) undergoing surgery
2. Age $<$ 18 years
3. ECOG >2
4. Life expectancy <6 months
5. Not signed informed consent

Study Duration	Each subject's participation will last from inclusion (enrolment visit) to follow up visit (if applicable; four weeks post hospital discharge) The entire study is expected to last by the end of 2019
Study Phases	(1) Screening : screening for eligibility, obtaining consent and administer thromboprophylaxis
Screening	
Study Treatment	(2) Observation Period : monitoring subjects over treatment time
Treatment	(3) Follow-up Phase (only if applicable e.g. by the end of treatment period)
Follow-Up	
Efficacy Evaluations	
 • Symptomatic/Suspected vein thromboembolism, including pulmonary embolism and deep vein thrombosis 
Confirmation of symptomatic PE requires symptoms of PE and one of the following findings
 
 1. A (new) intraluminal filling defect in (sub) segmental or more proximal branches on spiral CT scan; 2. A (new) intraluminal filling defect or an extension of an existing defect or a new sudden cut-off of vessels on the pulmonary angiogram;

3. A (new) considerable perfusion defect (~ 75% of a segment) with a local normal ventilation result (high-probability) on ventilation/perfusion lung scintigraphy (V/Q scan);
4. An inconclusive lung scan accompanied by documentation of (new) DVT in the lower extremities e.g., by compression ultrasound or venography.
 - Confirmation of symptomatic DVT requires symptoms of DVT and:
 - 1. A (new) noncompressible venous segment on ultrasonography
 - Incidental PE with one of the following:
 1. A (new) intra-luminal filling defect on CT scan, MRI scan, or pulmonary angiogram;
 - An inconclusive lung scan accompanied by documentation of (new) DVT in the lower extremities e.g., by compression ultrasound or venography.
 - Fatal PE is:
 1. PE based on objective diagnostic testing or autopsy or
 2. death not attributed to a documented cause and for which DVT/PE cannot be ruled out
 - Incidental DVT with the following finding:

Confirmation of recurrent incidental DVT requires inconclusive or no-symptoms of DVT and:

1. A (new) noncompressible venous segment on ultrasonography

Safety Evaluations Major, clinically relevant non-major bleeding, and minor bleeding

Major bleeding will be defined as overt bleeding associated with: a fall in hemoglobin of 2 g/dL or more, or leading to a transfusion, or bleeding that occurs in a critical site or contributing to death.

- **Bleeding in a critical area or organ such as:**

Retroperitoneal

Intracranial

Intraocular

Intraspinal

Intra-articular

Pericardial

Intramuscular with compartment syndrome

- **A clinically overt bleeding event**
 - that is associated with a fall in hemoglobin of 2.0 g/dL (>1.24 mMol/L) or more, or
 - leading to a transfusion of ≥ 2 units of packed red blood cells or whole blood.
- **Bleeding contributing to death**

Other clinically relevant non-major bleeding will be defined as overt bleeding not meeting the criteria for major bleeding but associated with medical intervention, unscheduled contact (visit or telephone call) with a physician, (temporary) cessation of study treatment, or associated with discomfort for the patient such as pain, or impairment of activities of daily life. All other bleeding events will be classified as minor

Statistical And Analytic Plan	
Descriptional statistical analysis will be performed for all study data along with epidemiology methods. Continuing parameters will be presented with standards descriptional statistical measures (mean values, median values, percentages etc.) and the results will be presented accordingly into tables. For more complex correlations we will use, among other methods, chi-square tests, ANOVA and t-tests, in order to evaluate the relationships between different patient and disease characteristics, such as:
 
 • Number of patients enrolled • Tumor characteristics • Co-morbidities • Type of Surgical operation • Type of antineoplastic treatment • Type of thromboprophylaxis therapy • Therapy outcomes • Number of therapy disruptions for any reason • Complications (AE- SAE) 
and to present them, accordingly. Due to the fact that this is an observational study the results of all correlations will be carefully discussed and will be used only to assess hypotheses.

REFERENCES	References

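### The plan sets no enrolment closing date or minimum follow-up before the common study end, and no method for prophylaxis courses still ongoing at that point

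*Combined protocol and SAP*

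**What the plan says.** Three places set the calendar. The Study Objective collects data "for one year following the protocol initiation date". The Study Design describes a cohort "initiated December 2018 for a year time". Study Duration adds "The entire study is expected to last by the end of 2019". None gives a date on which enrolment closes.

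Two places set the individual patient's time. Under Study Duration, participation runs from inclusion "to follow up visit (if applicable; four weeks post hospital discharge"). Under Study Phases, the observation period means "monitoring subjects over treatment time", with no fixed length.

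Subject Completion/Withdrawal lists, among the reasons for discontinuing a patient, "or due to termination of study observation period". The same section says that completion or non-completion will be documented for each patient.

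The objectives include the number of thrombotic events and "Anti-thrombotic management dosage & duration". The Statistical And Analytic Plan is descriptive. It names means, medians and percentages, with chi-square tests, ANOVA and t-tests for relationships between characteristics. It names no censoring, time-to-event or person-time method, and gives no rule for incomplete courses.

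**The concern.** If patients can enter close to the common stop, some will still be on prophylaxis when data collection ends. Their recorded duration is the time to the stop, not the length of the course. Without a rule for such courses, that shorter figure goes into the mean with the completed ones, and events after the stop are not seen.

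The loss is uneven. Short courses are nearly all complete by the stop, while long ones are cut more often. The planned comparisons by type of antineoplastic treatment and type of thromboprophylaxis could therefore partly reflect how much of each course was observed. The later weeks also matter for events: the protocol's background cites a prospective cancer-surgery cohort in which 40% of symptomatic VTE occurred more than 3 weeks after surgery.

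**Working it through.** The plan states no sample size, accrual period or event rate, so there is no figure of its own to reproduce. The check asks how much truncation the stated dates allow.

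**Inputs from the documents**
- Start: December 2018, day not given.
- End: by the end of 2019. From 1 December 2018 to 31 December 2019 is 395 days; from 31 December 2018 it is 365 days. So T = 365 to 395 days.
- The one-year mark falls 0 to 30 days before the end of 2019.
- Surgical follow-up: a visit four weeks after discharge.

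**Assumptions**
- Entry is uniform over the first A days, and everyone still under observation is closed at day T.
- Each patient has a full course of D days. D = 35 is 28 days plus an assumed 7-day stay. D = 90 and D = 180 stand for long courses; the documents give no chemotherapy course length.

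**Formulas.** Let G = T − A be the gap between the last entry and the stop. For D > G:
- share truncated = (D − G) / A
- mean shortfall, as a fraction of D = (D − G)² / (2 × A × D)

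With G = 0 these reduce to D/T and D/(2T).

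**Case 1: enrolment runs to the stop (A = T, G = 0)**

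| D (days) | Truncated, T = 365 | Truncated, T = 395 | Mean short, T = 365 | Mean short, T = 395 |
|---|---|---|---|---|
| 35 | 35/365 = 9.6% | 35/395 = 8.9% | 35/730 = 4.8% | 35/790 = 4.4% |
| 90 | 24.7% | 22.8% | 12.3% | 11.4% |
| 180 | 49.3% | 45.6% | 24.7% | 22.8% |

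**Case 2, the favourable one: enrolment closes at one year and data collection runs 30 days longer (A = 365, T = 395, G = 30)**

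| D (days) | Truncated | Mean short |
|---|---|---|
| 35 | 5/365 = 1.4% | 5²/(2 × 365 × 35) = 0.1% |
| 90 | 60/365 = 16.4% | 60²/(2 × 365 × 90) = 5.5% |
| 180 | 150/365 = 41.1% | 150²/(2 × 365 × 180) = 17.1% |

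**Median.** With one fixed course length, the median stays at D while fewer than half are truncated. That holds in every row above (maximum 49.3%), so these figures show bias in the mean only. Course lengths that vary between patients could move the median too, but the documents do not allow that to be sized.

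**After the change.** If the last entry is at day T − D, both truncation and shortfall are zero. For a stop at day 365 that is day 330, 275 or 185 (D = 35, 90, 180). For a stop at day 395 it is day 360, 305 or 215.

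**The case against.** The strongest reply is that the documents never say enrolment continues to the last day. A reader might infer that enrolment and observation stop together, so that everyone entering in the last quarter of 2019 is cut off. That is an inference from silence. The end date is only an expectation, and the participation rule just before it gives each patient an individual end point. With a stop on 31 December and 35 days of participation, a surgical patient entering as late as 26 November still reaches the visit. This stands, and it is why case 2 is shown.

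Second, the discontinuation reason "due to termination of study observation period" may refer to the patient's own observation phase, since Study Phases uses the term that way. The wording leaves this open. The calendar reading is the more natural one, because reaching the end of one's own observation would be completion and not discontinuation.

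Third, the larger percentages depend on assumed chemotherapy courses. The first inclusion criterion names only patients undergoing surgery, although the Study Objective and Study Design include chemotherapy. This also stands: the figures for 90 and 180 days illustrate the effect and are not estimates for this cohort.

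Fourth, non-completers will be documented, and the analysis section leaves room for unspecified epidemiological and other methods. Incomplete patients may thus be identifiable, and the case report form, listed only by title, may record ongoing treatment. But being able to identify them is not a rule for analysing them, and the plan states none.

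Finally, a reader might infer that adherence is biased in a known direction as well. Nothing in the documents shows a direction for adherence.

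**Conclusion.** The point holds in limited form. The plan has a common stop with no enrolment closing date or minimum follow-up before it, two rules for the end of participation that are not reconciled, and no method for courses still open at the stop. Applied as written, it can understate mean prophylaxis duration and miss later VTE and bleeding.

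Over the two enrolment cases, the mean is 0.1 to 5% short for a surgical participation of about 35 days, which is minor. It is 5.5 to 12% short for a 90-day course and 17 to 25% short for a 180-day course. The long-course figures are material and do not disappear in the favourable case. All rest on uniform entry, a single course length per scenario and a hard stop between day 365 and day 395. The stronger claim, that late entrants are certain to be lost, is not supported. The change is worth making because it is cheap and because duration and thrombotic events are stated objectives.

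**What to change.** **Design.** State a last-enrolment date that lets each patient finish the participation period before the stop, or state that data collection continues until the last enrolled patient has done so. Say how the four-week visit and the treatment-time observation period relate to the calendar end.

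**Recording.** Keep end-of-study closure as a recorded reason, defined as administrative censoring, separate from both withdrawal and completion. Removing it would leave nothing to censor on. Record start and stop dates of prophylaxis, and flag courses ongoing at database close.

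**Analysis.** Report prophylaxis duration by Kaplan-Meier with ongoing courses censored. Report VTE and bleeding per person-time or as cumulative incidence, alongside the raw counts.

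**Cost.** The change needs protocol wording, a little more analysis work, and either a somewhat later database lock or a smaller cohort. No new patient procedures are needed. If the end date is fixed, closing enrolment early forgoes the same share of patients as would have been truncated: 1 to 10% for a 35-day participation, but 16% or more for a 90-day course. For long courses, continued collection or censoring is therefore the cheaper route. The recording and analysis changes can be made even if no date moves.
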